Background: Children with cerebral palsy (CP) frequently struggle with gross motor function, which can interfere with their daily activities and quality of life. Although physiotherapy is an important intervention for improving gross motor function in children with cerebral palsy, adherence to treatment remains a challenge. Physiotherapy programs based on play therapy have been proposed as a new alternative approach to improving treatment adherence and gross motor function in children with cerebral palsy. The aim of this research protocol is to compare the efficacy of play therapy-based physiotherapy programs compared to traditional physiotherapy programs in improving treatment adherence and gross motor function in children with CP GMFCS level III-IV.

Methods: This study will be a randomized controlled trial with a sample size of 64 children aged 4-12 with CP GMFCS level III-IV. Participants will be randomly assigned to receive either a play therapy-based physiotherapy or conventional physiotherapy program 45 minutes twice a week for a period of 16 weeks. Treatment adherence will be measured using a combination of physiotherapy session attendance rates, an adherence logbook and the Goal Attainment Scale (GAS). Gross motor function will be assessed using the Gross Motor Function Measure (GMFM-88) and Quality of life will be measured using the CPQoL-Child, all this will be measured at baseline, 5 weeks, 10 weeks and 16 weeks of intervention and a follow-up at 24 weeks will be done. Data will be analysed using descriptive statistics, independent t-tests, ANCOVA and correlations.

Key words: infantile cerebral palsy, play-therapy, treatment adherence, gross motor function, quality of life and physiotherapy.

3. Título

La eficacia de los programas de fisioterapia basados en la terapia de juego frente a los programas de fisioterapia convencionales para mejorar la adherencia al tratamiento y la función motora gruesa en niños con parálisis cerebral GMFCS nivel III-IV: un protocolo de investigación para un ensayo controlado aleatorizado.

4. Resumen

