9.2.5. Randomization

Participants will be randomly assigned to either the experimental group (play therapy-based physiotherapy program) or the control group (conventional physiotherapy program). However, to guarantee group balance, randomization might be stratified by age, gender and GMFCS level. In addition, allocation concealment will be applied to reduce the risk of bias for the outcome assessors.

To do the stratified randomization, first participants will be categorized by the level of GMFCS (III or IV). Then, they will be divided into two subgroups according to age (4-7 years and 8-12 years) and inside these subgroups they will be divided by gender (male and female). Within each stratum, participants will be randomly allocated to either group using a computer-generated randomization list created by an independent statistician who will not be involved in the study.

A. Palisano R, et al. Development and reliability of a system to classify gross motor function in children with cerebral palsy. *Dev Med Child Neurol.* 1997 Apr;39(4):214-23.

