9.5. Data Collection

Many steps will be applied during the study to guarantee the security and confidentiality of participants' data. To begin, all data obtained will be kept totally secret and only authorized members of the study team will have access to it. To do the allocation concealment, a statistician will generate the randomization list by given to participants a unique identification number, which will be used to assign them to one or another group.

For the outcome measure assessment different procedures will be conducted. The GAS, the GMFM-88 and the CP QoL-Child will be done at baseline, after 5, 10 and 16 weeks and at the follow-up assessment at 24 weeks. In the baseline the GAS will be used as a way for the physiotherapist to plan the intervention and in the mid-term assessments the goals achievement will be measured, all this by the physiotherapist. The GMFM-88 will be assessed by the outcome assessor and the CP QoL-Child will be done by parents or caregivers who will give the questionnaire to the research assistants for them to score it and save it.

On the other hand, the logbook will be completed by the physiotherapist after each participant session and at the end of the 16 weeks intervention will be given to the research assistants to do the data collection and after that, the analysis.

All paper-based data will be stored in locked cabinets in a secure research facility and electronic data will be kept on a password-protected computer and will be stored and managed from Microsoft One Drive cloud, which contains a double security system. Exclusively authorized people will be able to access to the data.

Only de-identified data will be shared in any publications or presentations emerging from the study to protect the privacy and confidentiality of participants. Without express written authorization, participants' personal data will not be shared with anybody outside of the study team.

Once all the study is finished, the obtained data may be maintained for a limited time, as needed by institutional guidelines, before being securely deleted to prevent unauthorized access or use. Overall, the research team is committed to maintaining the greatest levels of privacy and confidentiality to protect the safety and well-being of all study participants.

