9.6. Data Analysis

All data collected from the assessments, questionnaires and the logbook will be analysed using appropriate statistical methods with the help of an expert statistician to achieve the aims of this research protocol. The statistical analyses will be conducted using a statistical software package such as JASP and the statistical significance will be set at p-value <0.05 and CI (Confidence Interval) 95%. When p-value $< 0,05$, the null hypothesis (H_0) will be rejected meaning that the results are statistically significant. The H_0 is: There is no significant difference between the effectiveness of play therapy-based physiotherapy programs and conventional physiotherapy programs in improving treatment adherence and gross motor function in children with cerebral palsy GMFCS level III-IV.

After collecting all data, it will be placed into a spreadsheet for basic data cleaning and categorization ([Annex V](#)). Descriptive statistics (e.g., mean, median, standard deviation, range...) will be calculated to summarize quantitative variables such as age, attendance rate, treatment adherence logbook, GAS score, GMFM-88 score and CP QOL-Child score, while frequency distributions and percentages will be used to summarize categorical variables such as gender, GMFCS level (III or IV), socio-economic status, ethnicity, and type of intervention. All that describes the participants' demographic and baseline characteristics, as well as analyses the distribution of the variables of interest.

Statistical analysis will be done to test the hypothesis using appropriate methodologies based on the data distribution and characteristics. For quantitative variables, t-tests or ANOVA may be used to compare means between the two groups (play therapy-based physiotherapy versus conventional physiotherapy). However, for categorical variables, chi-square or Fisher's exact test might be used, but in this study, it may not be necessary as the hypothesis doesn't include categorical variables.

Moreover, linear regression analysis may be used to investigate the association between treatment adherence and gross motor function while to identify predictors of treatment adherence, gross motor function and quality of life, including age, gender, GMFCS level, social-economic status, ethnicity, and treatment group so potential confounding variables will be controlled for in the

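### Section 9.6 and the abstract name different between-group tests, and no model in 9.6 uses the baseline score, so available precision for GMFM-88 and CP QoL-Child is left unused

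*Protocol*

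**What the plan says.** The English abstract states: "Data will be analysed using descriptive statistics, independent t-tests, ANCOVA and correlations". The Spanish abstract (section 4) lists the same methods. Section 9.6, on testing the hypothesis, says that for quantitative variables "t-tests or ANOVA may be used to compare means between the two groups". ANCOVA does not appear in 9.6, and Annex V assigns only descriptive statistics to each variable.

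Section 9.6 also offers, again as an option, linear regressions that look for predictors of each of the three outcomes. Their covariates are given as follows: "including age, gender, GMFCS level, social-economic status, ethnicity, and treatment group so potential confounding variables will be controlled for in the" (the sentence then ends by naming that model). The baseline score of the outcome is not in that list.

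On what is collected, section 9.5 says: "The GAS, the GMFM-88 and the CP QoL-Child will be done at baseline, after 5, 10 and 16 weeks", with a further assessment at week 24. For GAS it adds: "In the baseline the GAS will be used as a way for the physiotherapist to plan the intervention". For adherence, "the logbook will be completed by the physiotherapist after each participant session".

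Section 9.2.5 says that "randomization might be stratified by age, gender and GMFCS level", then describes strata by GMFCS level (III or IV), age band (4-7 or 8-12 years) and gender, with a computer-generated list within each stratum. It mentions no blocking.

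**The concern.** The document gives two different answers to the question of which test decides the trial. In the section that should settle it, the tests named carry no covariate. Objective II and the hypothesis concern improvement in gross motor function, and the starting score of each child is known, yet no model in 9.6 uses it.

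At stake is precision, not validity. In a randomized trial an unadjusted comparison of means is unbiased. However, baseline adjustment reduces the residual variance when the baseline predicts the outcome, and it removes chance baseline imbalance from the estimate. With 32 children per group there is little precision to spare. Leaving both an adjusted and an unadjusted test open also lets the choice be made after the data are seen.

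**Working it through.** **Inputs**
- SD 2.43, d 1.2, z-values 1.96 and 0.8416: Annex I.
- 32 per group: section 9.2.1.
- Two-sided alpha 0.05: section 9.6 ("statistical significance will be set at p-value <0.05 and CI (Confidence Interval) 95"%) and the alpha/2 in Annex I.
- Correlation r between baseline and week-16 score: not in the document. Assumed, range 0.3 to 0.8.

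**Step 1: the plan's own figure.** n = 2 × 2.43² × (1.96 + 0.8416)² / 1.2² = 64.37, as Annex I states. This formula gives a number per group, whereas the plan has 32 per group. That is a separate matter, but it sets the power from which the rest starts.

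**Step 2: unadjusted test.** Annex I uses d as a raw difference, so the standardised effect is 1.2 / 2.43 = 0.494. The standard error of the difference is 2.43 × √(2/32) = 0.608. Power by the noncentral t with 62 degrees of freedom is 49%.

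**Step 3: ANCOVA, if 2.43 is the SD of the raw score.** The residual variance is multiplied by 1 − r², so the effect becomes 0.494 / √(1 − r²).

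**Step 4: ANCOVA, if 2.43 is the SD of change.** The variance of change is 2σ²(1 − r) and the ANCOVA residual variance is σ²(1 − r²). Their ratio is (1 + r)/2, so the effect becomes 0.494 / √((1 + r)/2), to be compared with 49% for a change-score test.

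| r (assumed) | Step 3: variance factor | Step 3: power | Step 4: variance factor | Step 4: power |
|---|---|---|---|---|
| 0.3 | 0.91 | 53% | 0.65 | 67% |
| 0.5 | 0.75 | 61% | 0.75 | 61% |
| 0.7 | 0.51 | 78% | 0.85 | 56% |
| 0.8 | 0.36 | 90% | 0.90 | 54% |

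The table counts one covariate. Adding the three stratification factors to the degrees of freedom changes power by about 0.1 percentage point. Any variance that they explain would be a further gain and is not counted.

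**Step 5: which outcomes can gain from a baseline.** GMFM-88 and CP QoL-Child have a true baseline score. The logbook and attendance arise only during treatment. GAS at baseline sets goals, and attainment is scored later. Baseline adjustment therefore does nothing for the adherence half of the primary outcome.

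**Step 6: the strata, conditionally.** If allocation is balanced within strata and the factors explain a share R² of the variance (assumed), the true type I error of a nominal 5% unadjusted test is 2 × [1 − Φ(1.96/√(1 − R²))]. This gives 3.9%, 2.8% and 1.9% at R² of 0.1, 0.2 and 0.3. The test is then conservative. Without balance within strata this does not follow.

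**The case against.** The strongest reply is that nothing is fixed. The tests in 9.6 are permissive, the choice is tied to the data distribution, the abstract does name ANCOVA, and a covariate list is commonly left to a statistical analysis plan, which is not shown here. This stands against any claim that the protocol commits itself to an unadjusted test. It does not remove the conflict between the abstract and 9.6, or the fact that the one covariate list in 9.6 omits the baseline score.

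Several stronger readings are tempting, but the document does not support them:
- **That the stratification factors are ignored.** The optional regression contains all three together with treatment group, for adherence, motor function and quality of life. It is simply not declared the hypothesis test.
- **That post-treatment means are compared.** Section 9.6 says only that means are compared. The references to improvement leave change scores equally open, which is why Step 4 is needed.
- **That between-child spread in GMFM-88 dominates the comparison.** The protocol gives no figure for spread at GMFCS III and IV, and Annex I does not tie 2.43 to GMFM-88.
- **That the standard error is too large for the design.** This needs balance within strata. Section 9.2.5 makes stratification a possibility and states no blocking, and simple randomization within strata does not force balance.
- **That GAS could serve as a baseline covariate.** At baseline it is a planning tool.

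It is also fair to say that the low starting power comes from using a per-group number as the total. Baseline adjustment eases that problem but does not correct it.

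**Conclusion.** The point holds as an inconsistency to resolve and a gain in precision available at no cost; it is not a charge of invalid analysis. Section 9.6 and the abstract disagree on the test, and no model in 9.6 uses the baseline GMFM-88 or CP QoL-Child score.

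The direction of the gain is secure for any appreciable correlation below 1, but its size is not. Under the raw-score reading, power at 32 per group goes from 49% to between 53% and 90% over r = 0.3 to 0.8. Under the change-score reading it goes to 61%, 56% and 54% at r = 0.5, 0.7 and 0.8, so the gain is small when the correlation is high. These figures rest on an assumed r and on Annex I's 2.43 and 1.2, for which the annex names neither the outcome nor the kind of SD. The gain concerns GMFM-88 and CP QoL-Child only.

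**What to change.** In section 9.6:
- Name the primary GMFM-88 analysis as ANCOVA of the week-16 score on treatment, baseline GMFM-88, GMFCS level, age band and gender.
- Use the same model for CP QoL-Child with its own baseline.
- For attendance, logbook score and GAS attainment, which have no usable baseline, adjust for the three stratification factors only. Do not use GAS as a baseline covariate.
- Report adjusted differences with 95% confidence intervals.
- Replace the permissive wording for the hypothesis test with this single choice, and make the English and Spanish abstracts agree with it.

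In Annex I, state which outcome the SD of 2.43 belongs to and whether it is an SD of the score or of change.

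The cost is wording only. Every covariate is already collected, at screening or at the baseline assessment.

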8.1. General Objective

To compare the effectiveness of play therapy-based physiotherapy programs versus conventional physiotherapy programs in improving treatment adherence and gross motor function in children with cerebral palsy GMFCS level III-IV over a 24-week period.

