9.2. Participants, Recruitment and Criteria of Selection

9.2.1. Participants

The participants of this research will be children with CP GMFCS level III-IV, aged 4 to 12 years and receiving physiotherapy services.

For the sample size ([Annex I](#)), help will be requested from a statistician, and it will depend on factors such as the expected effect size based on previous studies or clinical knowledge, the level of statistical power desired and the level of significance. For example, knowing that similar studies have a sample size of 30, which is always their limitation, a medium effect size is expected, a power of 80% is desired and 0.5 is considered as the level of significance, a sample size of around 64 participants (32 in each group) might be appropriate. However, this sample size might need to be adjusted based on the recruitment rate, dropout rate, and effect size observed during the study.

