15.1. Annex I: Calculation of the Sample Size

For calculating the sample size the following formula have been used (F, G):

$$n = \frac{2SD^2(Z_{\alpha/2} + Z_{\beta})^2}{d^2}$$

Where:

- **n** = sample size
- **Z $\alpha/2$** = the Z-score for the desired level of significance so for 95% confidence level $\alpha=0.05$, $Z_{\alpha/2} = 0.05/2 = 0.025$. This from Z table is **1.96**.
- **Z β** = the Z-score for the desired statistical power so for 80% power where β is 0.20, $Z_{\beta} = 0.8416$ from the Z table.
- **SD** = the estimated standard deviation of the outcome variable based on other studies is **2.43** (18).
- **d** = the effect size (difference in means divided by the pooled standard deviation) taking into account the previous study (18) it will be **1.2**.

Having into account all this, the sample size should be:

$$n = \frac{2SD^2(Z_{\alpha/2} + Z_{\beta})^2}{d^2}; n = \frac{2 \times 2.43^2 (1.96 + 0.8416)^2}{1.2^2}; n = 64.37 \approx 64 \text{ participants}$$

Sample size = 64 participants.

Remember that this sample size may need to be adjusted by a statistician based on factors such as recruitment rate and expected dropout rate.

F: Charan J, Biswas T. How to calculate sample size for different study designs in medical research? Indian J Psychol Med. 2013 Apr;35(2):121-6.
G. Kadam P, Bhalerao S. Sample size calculation. Int J Ayurveda Res. 2010 Jan;1(1):55-7.

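### GMFM-88, CP QoL-Child and GAS are scheduled at four visits after baseline, but the tests named have no repeated-measures term; used at one visit, they drop children who miss it.

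*Protocol*

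**What the plan says.** Section 9.5 states that GAS, GMFM-88 and CP QoL-Child "will be done at baseline, after 5, 10 and 16 weeks and at the follow-up assessment at 24 weeks", which makes four post-baseline visits. The general objective in section 8.1 is a comparison "in children with cerebral palsy GMFCS level III-IV over a 24-week period".

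For the hypothesis test, section 9.6 says that "t-tests or ANOVA may be used to compare means between the two groups". It adds that "linear regression analysis may be used to investigate the association between treatment adherence and gross motor function", and extends the regression to predictors of adherence, motor function and quality of life. The abstract's list differs slightly: "Data will be analysed using descriptive statistics, independent t-tests, ANCOVA and correlations". ANCOVA appears only there.

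The protocol describes no repeated-measures or mixed model and no group-by-visit term. It does not name the visit to be tested or say what happens to a child who misses it. Annex V lists only descriptive statistics for these variables.

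**The concern.** Each named test, as described, needs one value per child. The ordinary use is to test one visit. A child absent then contributes nothing, even with scores from weeks 5 and 10, and no child's other post-baseline scores enter the test.

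Two things are at stake. The first is precision, in a trial of only 64 children. The second matters more. A complete-case comparison at one visit is safe if the children lost are like those retained, but it may be biased if loss depends on earlier scores and differs between arms. The trial's own hypothesis is that adherence differs by arm, so unequal, score-related loss cannot be dismissed.

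**Working it through.** **Inputs from the protocol.** There are 32 children per arm (section 9.2.1), SD 2.43 and difference 1.2 (Annex I), so 1.2/2.43 = 0.494 SD. The test is two-sided at 0.05, as in section 9.6 ("statistical significance will be set at p-value <0.05 and CI (Confidence Interval) 95") and Annex I; section 9.2.1 prints 0.5, which conflicts with both.

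**The plan's own figure.** 2 × 2.43² × (1.96 + 0.8416)² / 1.2² = 64.37, so Annex I's 64 reproduces. That formula gives a number per arm, whereas the protocol uses it as the total. This is a separate issue, but it means that a single-visit t-test with 32 per arm and nothing missing has about 49% power (noncentral t).

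**Assumptions.** The documents give no within-child correlation and no dropout rate. I take equal correlation r between visits, from 0.5 to 0.9, a fraction m = 0.15 missing at weeks 16 and 24, and weeks 5 and 10 observed for everyone.

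**Week-16 contrast, no baseline adjustment.** Two earlier visits explain a share R² = 2r²/(1 + r) of the week-16 variance. The variance of the mixed-model contrast relative to the complete-case test is 1 − m·R².

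| r | R² | variance ratio | SE lower by |
|---|---|---|---|
| 0.5 | 0.333 | 0.950 | 2.5% |
| 0.7 | 0.576 | 0.914 | 4.4% |
| 0.9 | 0.853 | 0.872 | 6.6% |

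**Baseline adjustment in both analyses.** Given baseline, the correlation between visits becomes p = r/(1 + r), and R² = 2p²/(1 + p).

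| r | p | R² | variance ratio | SE lower by |
|---|---|---|---|---|
| 0.5 | 0.333 | 0.167 | 0.975 | 1.3% |
| 0.7 | 0.412 | 0.240 | 0.964 | 1.8% |
| 0.9 | 0.474 | 0.305 | 0.954 | 2.3% |

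With m = 0 both ratios are 1: the week-16 contrast gains nothing.

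**Bias, as a worst case.** Suppose one arm loses the 15% of children who scored lowest at an earlier visit, and the other arm loses none. The earlier-visit mean of those retained rises by φ(−1.036)/0.85 = 0.233/0.85 = 0.274 SD. The complete-case week-16 mean then rises by r × 0.274, which is 0.14 SD at r = 0.5 and 0.25 SD at r = 0.9, against a planned effect of 0.494 SD. A likelihood-based model that includes the earlier visit removes bias of this kind, because the loss depends only on observed scores.

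**The case against.** The wording is permissive. The tests are ones that may be used, a statistician is to help, and a statistical analysis plan that is not shown could set out the longitudinal model. A t-test can be run on a per-child summary over visits, and ANOVA can include visit as a factor. This stands to the extent that the protocol does not say that groups are compared one visit at a time or that absent children are dropped; both follow from ordinary use of the tests named. But the protocol does name its tests, in two places, and neither list is fitted to its own visit schedule. If ANOVA meant the classical repeated-measures form, listwise deletion would drop more children: with 10% missing independently at each visit, 0.9⁴ = 66% would be complete over four visits.

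A reader might infer that section 8.1 requires an average over the four visits. It does not: the 24 weeks can equally be read as the study's duration, and neither the hypothesis nor the null hypothesis defines such an average.

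A reader might also expect a large gain in power from averaging the visits. The SE of a four-visit mean relative to one visit is √((1 + 3r)/4) = 0.88 at r = 0.7, and power would rise from 49% to 60% if the full 0.494 SD difference were present at every visit. Nothing in the documents supports full effect by week 5 or full retention at week 24, eight weeks after the intervention ends. If instead the effect built linearly to week 16 and was kept at week 24, the average effect would be (5/16 + 10/16 + 1 + 1)/4 = 0.734 of it, and power for the average would be 37% at r = 0.7, below that for week 16 alone.

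Finally, baseline adjustment gives more precision than the mixed model. At r = 0.7 with 20% missing (normal approximation), it takes power from 42.3% to 69.6%, and the mixed model then adds about 2 points, to 71.8%. ANCOVA in the abstract could supply that adjustment if baseline is its covariate. This stands, and limits the precision argument.

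**Conclusion.** The point holds in a limited form. The named tests do not fit the visit schedule; applied to a single visit, they discard children with usable earlier scores and make no use of the other post-baseline visits. The like-for-like gain in precision at week 16 is modest, and it rests on the assumed 15% missing, equal correlations and observed weeks 5 and 10.

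The case therefore rests mainly on three things: keeping children who miss a visit, remaining valid when loss depends on earlier observed scores, and taking every visit contrast from one model. The size of any bias cannot be known from the documents; 0.14 to 0.25 SD is a deliberately unfavourable illustration. The change should be made, but not on the promise of a large gain in power.

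**What to change.** In section 9.6, for GMFM-88 and CP QoL-Child, name one linear mixed model on all available post-baseline visits (weeks 5, 10, 16 and 24). Include group, visit, group × visit, baseline score with baseline × visit, and the stratification factors. Use an unstructured within-child covariance, a stated simpler structure if it does not converge, and a small-sample degrees-of-freedom correction. Check whether GAS, which has the same schedule, should be handled in the same way.

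Take the primary contrast from this model at one visit named in advance, for example week 16, the end of the intervention. Report the other visits and any average over visits as secondary. Bring the abstract's list of tests into line.

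The cost is analysis wording, a little more programming and reliance on a missing-at-random assumption, which the data cannot verify. No new data are needed.

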8.2. Specific Objectives

- I. To compare treatment adherence among children receiving game-based physiotherapy and those receiving conventional physiotherapy.
- II. To evaluate improvements in gross motor function among children receiving game-based physiotherapy and those receiving conventional physiotherapy.
- III. To compare quality of life between children receiving game-based physiotherapy and those receiving conventional physiotherapy.
- IV. To identify potential factors that may influence quality of life, treatment adherence, and improvements in gross motor function in both treatment groups.

9. Methodology

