regression model. In addition, for identifying predictors of treatment adherence each part of the logbook will be analysed in this same way.

Lastly, the findings will be presented concisely and understandably, using tables and graphics and conclusions will be formed based on the statistical significance.

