The applicability and usefulness of this project's outcomes are important for multiple reasons. To begin, cerebral palsy is a chronic disorder that impairs children's ability to move, perform daily tasks and participate in life. Physiotherapy is a significant part of cerebral palsy treatment since it tries to enhance function and minimize secondary complications. When compared to conventional physiotherapy, the use of play-based physiotherapy has been suggested as a potentially more successful strategy to engage children in therapy and promote treatment adherence while improving gross motor function. So, the results of this randomized controlled study will aid in determining if the hypothesis is correct. That's why if the study reveals that is more successful, it might have significant implications for the development of new interventions and treatment protocols for children with CP, which is the main goal of this project.

Furthermore, the identification of potential factors that may influence treatment outcomes is also valuable for improving treatment approaches in the future. By identifying these potential factors, physiotherapists can develop more tailored treatment plans considering the unique needs and circumstances of each patient. All in all, this can help to improve treatment outcomes and ensure that they receive the most effective and tailored physiotherapy program. For example, if this study shows that children from poor socioeconomic status or an specific ethnic group respond better to play therapy-based physiotherapy program or vice versa, physiotherapist may adapt treatment techniques to these specific populations to be more tailored and equitable.

Lastly, in case that the hypothesis is found to be wrong, the methodology of the study, including the inclusion and exclusion criteria and the use of stratified randomization, will add to the domain of cerebral palsy research and serve as a model for future studies as well as the study's emphasis on incorporating individuals from a variety of socioeconomic situations and ethnicities will assist to guarantee that the findings are applicable to a broad range of children with cerebral palsy. Moreover, the study's attention on ethical issues, such as getting informed consent and providing fair access to the study, will contribute to the general ethical standards and best practices in this field.

14. Dissemination Plan

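### The objective IV predictor regressions run 15 to 55 tests at a single p<0.05 and draw conclusions from significance; they should be labelled exploratory (minor)

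*Protocol*

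**What the plan says.** Objective IV (Protocol, Section 8.2) is "To identify potential factors that may influence quality of life, treatment adherence, and improvements in gross motor function in both treatment groups". Section 9.6 gives the method. Linear regression may be used "to identify predictors of treatment adherence, gross motor function and quality of life, including age, gender, GMFCS level, social-economic status, ethnicity, and treatment group". The next step widens the search: "In addition, for identifying predictors of treatment adherence each part of the logbook will be analysed in this same way".

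The same section sets one level for the analyses: "statistical significance will be set at p-value <0.05 and CI (Confidence Interval) 95" per cent. It closes by saying that "conclusions will be formed based on the statistical significance". The protocol does not call the predictor search exploratory and does not rank or adjust its tests.

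Section 13 states what the factors are for: "By identifying these potential factors, physiotherapists can develop more tailored treatment plans considering the unique needs and circumstances of each patient". Its example is that treatment techniques might be adapted if children of a given socio-economic or ethnic group were found to respond better to the play-based programme, or the reverse.

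**The concern.** Each patient factor in each regression gets its own test at 0.05, and the logbook sentence multiplies the number of regressions. When many such tests are run and significance decides the conclusion, some factors will be reported as predictors by chance alone. Chance findings are ordinary in a secondary analysis and do little harm if they are presented as leads. Here the protocol goes further: it ties conclusions to significance and names a clinical use, including adaptation by socio-economic status or ethnicity.

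The example in Section 13 adds a second problem. A better response to play therapy in one group is a treatment-by-factor interaction. The regressions in Section 9.6 list the factors and treatment group as predictors and name no interaction term. A significant coefficient for ethnicity, even a true one, would say that the outcome differs by ethnicity across both arms. It would not say that the treatments work differently.

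**Working it through.** The protocol gives no family-wise error figure for this search, so there is none to reproduce. The sample size used below is the protocol's 64 in total, 32 per arm. Annex I's arithmetic for it does reproduce: 2 × 2.43² × (1.96 + 0.8416)² / 1.2² = 64.37.

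**Inputs from the protocol**
- Level per test: 0.05 (Section 9.6). It is taken as two-sided because Annex I uses 1.96 for a 95% confidence level.
- Patient factors: age, gender, GMFCS level, socio-economic status and ethnicity, so 5 (Section 9.6). Treatment group is in the model but is not counted.
- Outcomes: adherence, gross motor function and quality of life, so 3 (Section 9.6).
- Logbook parts: 4 by the description in Section 9.4.1 (sessions completed, exercises done, the child's feelings, parents following advice), or 8 by the rows of Annex IV (attendance, session time, task completion, help, laughing, crying, anger, parents following advice).

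**Number of tests**
- Core: 5 × 3 = 15
- With 4 logbook parts: 5 × (3 + 4) = 35
- With 8 logbook parts: 5 × (3 + 8) = 55

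**If no factor has an effect and the tests are independent**, the chance of at least one false hit is 1 − 0.95^m and the expected number is 0.05 × m:
- m = 15: 1 − 0.95^15 = 53.7%; expected 0.75
- m = 35: 1 − 0.95^35 = 83.4%; expected 1.75
- m = 55: 1 − 0.95^55 = 94.0%; expected 2.75

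**With correlated outcomes** the chance of at least one hit falls, while the expected number stays the same. This was simulated with 4,000 null trials of 64 children per setting. Each outcome was regressed on age (4-12), gender, GMFCS level, socio-economic status (three levels, linear), ethnicity (binary, 25%) and arm, and every pair of outcomes had the same correlation. The coding and the correlations are assumptions; the protocol gives none.

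| Outcome correlation | 15 tests | 35 tests | 55 tests |
|---|---|---|---|
| 0 | 52% | 83% | 93% |
| 0.3 | 51% | 78% | 90% |
| 0.5 | 48% | 72% | 82% |
| 0.7 | 41% | 60% | 69% |
| 0.9 | 34% | 43% | 49% |

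Taking the independence formula as the upper end and correlation 0.9 as the lower, the ranges are 34-54%, 43-83% and 49-94%.

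**If some factors do matter**, fewer tests can give a false hit. Suppose, as an assumption, that 2 of the 15 core associations are real. Then 13 null tests remain: 1 − 0.95^13 = 48.7%, with 0.05 × 13 = 0.65 expected.

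**Not counted:** several coefficients for ethnicity or socio-economic status, GAS and attendance as further adherence measures, and repeated assessment times. Each would add tests.

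**The case against.** Much can be said for leaving the protocol as it is. How secondary regressions are labelled or adjusted is often settled in the SAP, which is not at hand. Section 9.6 says only that regression may be used. The one null hypothesis it spells out is the between-arm one, and the covariates also serve to control confounding. The factors are few, named in advance and motivated in the Background, which cites evidence that socio-economic status, ethnicity and gender bear on cerebral palsy and quality of life. The objective speaks of potential factors, and Section 9.7 admits that the sample is small. Section 13 says that physiotherapists can or may adapt care, not that they will.

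These points limit the size of the concern but do not remove it. Silence on adjustment alone would be no finding. What the protocol does state is the single threshold, the extension to each logbook part, the rule that conclusions follow significance, and the use of the factors. An adjustment in the SAP would leave the last two in place. The small-sample caveat in Section 9.7 is about generalising the results, not about chance findings.

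A reader might infer more than the documents support:
- That a false predictor is more likely than not. This requires that no factor has any effect, which the Background makes doubtful. Even then it fails for the 15 core tests at a correlation of 0.5 or above, and for 35 or 55 tests at 0.9.
- That 55 is the settled count. Section 9.4.1 supports 35 equally well. Logbook parts also make up the logbook total, so a common correlation is a simplification.
- That the error rate is many times the stated 5%. The protocol's 5% applies per test; it states no family-wise target to compare with.

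**Conclusion.** The point holds as a minor one. Section 9.6 fixes a multi-test predictor search, one p<0.05 and conclusions drawn from significance, and Section 13 puts the result to clinical use. Under a complete null, the chance of at least one false predictor runs from about a third (15 tests, correlation 0.9) to 94% (55 independent tests). True associations would lower it. The lasting features are the expected 0.75 to 2.75 chance hits under that null and the mismatch in Section 13, where main-effect regressions are offered in support of a claim about differential response. The mismatch does not depend on any of the assumed correlations. Neither the between-arm primary comparison nor its error rate is affected.

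**What to change.** In Section 9.6, state that all objective IV regressions, including those on parts of the logbook, are exploratory. Report coefficients with 95% CIs and the number of factor-by-outcome tests run, and exempt these analyses from the sentence that bases conclusions on significance. Say whether the logbook parts are the four components of Section 9.4.1 or the eight rows of Annex IV.

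In Section 13, describe any factors found as hypotheses for further study, and do not claim that a group responds better to one programme on the basis of main-effect regressions.

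A multiplicity adjustment such as Holm is optional. Unadjusted estimates with intervals, presented as exploratory, are an accepted alternative.

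The cost is a few sentences, with no extra children or data. The trial will be able to make fewer confident statements about individual factors.
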